**10.3.3. Recording and Follow-Up of AE and/or SAE**

AE and SAE Recording

 
• When an AE/SAE occurs, it is the responsibility of the investigator to review all documentation (eg, hospital progress notes, laboratory reports, and diagnostics reports) related to the event.
 
• The investigator will then record all relevant AE/SAE information in the CRF.
 
• It is not acceptable for the investigator to send photocopies of the participant's medical records to sponsor/designee in lieu of completion of the AE/SAE CRF page.
 
• There may be instances when copies of medical records for certain cases are requested by sponsor/designee. In this case, all participant identifiers, with the exception of the participant number, will be redacted on the copies of the medical records before submission to sponsor/designee.
 
• The investigator will attempt to establish a diagnosis of the event based on signs, symptoms, and/or other clinical information. Whenever possible, the diagnosis (not the individual signs/symptoms) will be documented as the AE/SAE.
 

Assessment of Intensity

The investigator will make an assessment of intensity for each AE and SAE reported during the study and assign it to 1 of the following categories:
 
 
• Mild: An event that is easily tolerated by the participant, causing minimal discomfort and not interfering with everyday activities.
 
• Moderate: An event that causes sufficient discomfort and interferes with normal everyday activities.
 
• Severe: An event that prevents normal everyday activities. An AE that is assessed as severe should not be confused with a SAE. Severe is a category utilized for rating the intensity of an event; and both AEs and SAEs can be assessed as severe.
 
 
An event is defined as 'serious' when it meets at least 1 of the predefined outcomes as described in the definition of an SAE, NOT when it is rated as severe.

Assessment of Causality

 
• The investigator is obligated to assess the relationship (Related or Unrelated) between study intervention and each occurrence of each AE/SAE.
 
• A "reasonable possibility" of a relationship conveys that there are facts, evidence, and/or arguments to suggest a causal relationship, rather than a relationship cannot be ruled out.
 
• The investigator will use clinical judgment to determine the relationship.
 
• Alternative causes, such as underlying disease(s), concomitant therapy, and other risk factors, as well as the temporal relationship of the event to study intervention administration will be considered and investigated.
 
• The investigator will also consult the Investigator's Brochure (IB) and/or Product Information, for marketed products, in his/her assessment.
 
• For each AE/SAE, the investigator must document in the medical notes that he/she has reviewed the AE/SAE and has provided an assessment of causality.
 
• There may be situations in which an SAE has occurred and the investigator has minimal information to include in the initial report to sponsor/designee. However, it is very important that the investigator always make an assessment of causality for every event before the initial transmission of the SAE data to sponsor/designee.
 
• The investigator may change his/her opinion of causality in light of follow-up information and send a SAE follow-up report with the updated causality assessment.
 
• The causality assessment is one of the criteria used when determining regulatory reporting requirements.
 

**Follow-up of AEs and SAEs**

- The investigator is obligated to perform or arrange for the conduct of supplemental measurements and/or evaluations as medically indicated or as requested by sponsor/designee to elucidate the nature and/or causality of the AE or SAE as fully as possible. This may include additional laboratory tests or investigations, histopathological examinations, or consultation with other health care professionals.
- If a participant dies during participation in the study or during a recognized follow-up period, the investigator will provide medical monitor with a copy of any post-mortem findings including histopathology.
- New or updated information will be recorded in the originally completed CRF.
- The investigator will submit any updated SAE data to the sponsor within 24 hours of receipt of the information.

**10.3.4. Reporting of SAEs****SAE Reporting to sponsor/designee via an Electronic Data Collection Tool**

- The primary mechanism for reporting an SAE to sponsor/designee will be the electronic data collection tool.
- If the electronic system is unavailable, then the site will use the paper SAE data collection tool (see next section) in order to report the event within 24 hours.
- The site will enter the SAE data into the electronic system as soon as it becomes available.
- After the study is completed at a given site, the electronic data collection tool will be taken off-line to prevent the entry of new data or changes to existing data.
- If a site receives a report of a new SAE from a study participant or receives updated data on a previously reported SAE after the electronic data collection tool has been taken off-line, then the site can report this information on a paper SAE form (see next section) or to the medical monitor/SAE coordinator by telephone.
- Medical Monitor can be contacted at: mobile [contact].  
Other contacts for SAE reporting can be found in the study manual.

**SAE Reporting to sponsor/designee via Paper CRF**

- Facsimile transmission of the SAE paper CRF is the preferred method to transmit this information to the medical monitor or the SAE coordinator.
- In rare circumstances and in the absence of facsimile equipment, notification by telephone or email is acceptable with a copy of the SAE data collection tool sent by overnight mail or courier service.
- Initial notification via telephone does not replace the need for the investigator to complete and sign the SAE CRF pages within the designated reporting time frames.
- Medical Monitor can be contacted at: mobile [contact].  
Other contacts for SAE reporting can be found in the study manual.

## 10.4. Appendix 4: Contraceptive Guidance and Collection of Pregnancy Information

### Definitions:

#### Woman of Childbearing Potential (WOCBP)

A woman is considered fertile following menarche and until becoming post-menopausal unless permanently sterile (see below).

If fertility is unclear (eg, amenorrhea in adolescents or athletes) and a menstrual cycle cannot be confirmed before first dose of study intervention, additional evaluation should be considered.

Women in the following categories are not considered WOCBP

1. Premenarchal
2. Premenopausal female with 1 of the following:
  - Documented hysterectomy
  - Documented bilateral salpingectomy
  - Documented bilateral oophorectomy

For individuals with permanent infertility due to an alternate medical cause other than the above, (eg, mullerian agenesis, androgen insensitivity), investigator discretion should be applied to determining study entry.

Note: Documentation can come from the site personnel's: review of the participant's medical records, medical examination, or medical history interview.

3. Postmenopausal female
  - A postmenopausal state is defined as no menses for 12 months without an alternative medical cause.
    - A high follicle stimulating hormone (FSH) level in the postmenopausal range may be used to confirm a postmenopausal state in women not using hormonal contraception or hormonal replacement therapy (HRT). However, in the absence of 12 months of amenorrhea, confirmation with more than one FSH measurement is required.
  - Females on HRT and whose menopausal status is in doubt will be required to use one of the non-estrogen hormonal highly effective contraception methods if they wish to continue their HRT during the study. Otherwise, they must discontinue HRT to allow confirmation of postmenopausal status before study enrollment.

**Contraception Guidance:**

Utilize an effective method of contraception from screening through to at least 4 weeks after the last dose of study drug, using one of the following: barrier methods (diaphragm or partner using condoms plus use of spermicidal jelly or foam, preferably double-barrier methods); oral or implanted hormonal contraceptive; intrauterine device (IUD); or vasectomized male partner

**Collection of Pregnancy Information:****Female Participants who become pregnant**

- The investigator will collect pregnancy information on any female participant who becomes pregnant while participating in this study. Information will be recorded on the appropriate form and submitted to the sponsor within 24 hours of learning of a participant's pregnancy.
- The participant will be followed to determine the outcome of the pregnancy. The investigator will collect follow-up information on the participant and the neonate and the information will be forwarded to the sponsor. Generally, follow-up will not be required for longer than 6 to 8 weeks beyond the estimated delivery date. Any termination of pregnancy will be reported, regardless of fetal status (presence or absence of anomalies) or indication for the procedure.
- While pregnancy itself is not considered to be an AE or SAE, any pregnancy complication or elective termination of a pregnancy will be reported as an AE or SAE. A spontaneous abortion is always considered to be an SAE and will be reported as such. Any post-study pregnancy related SAE considered reasonably related to the study intervention by the investigator will be reported to the sponsor as described in Section 8.3.4. While the investigator is not obligated to actively seek this information in former study participants, he or she may learn of an SAE through spontaneous reporting.

## 10.5. Appendix 5: Protocol Amendment History

The Protocol Amendment Summary of Changes Table for the current amendment is located directly before the Table of Contents (TOC).

### Amendment 1 (07-March-2019)

#### Overall Rationale for the Amendment:

This amendment incorporates comments provided by the FDA Study May Proceed letter (dated February 26, 2019), provides additional clarity, and addresses inconsistencies across the protocol.

Section # and Name	Description of Change	Brief Rationale
5.2 Exclusion Criteria #4	Significant moderate to severe hepatic insufficiency Changed to Significant moderate to severe hepatic insufficiency as defined by Child-Pugh B or C score	To define significant moderate or severe hepatic insufficiency according to the Child-Pugh scoring system described in the FDA Guidance for Industry: Pharmacokinetics in Patients with Impaired Hepatic Function: Study Design, Data Analysis, and Impact on Dosing and Labeling (2003)
10.2 Appendix 2: Clinical Laboratory Tests	Added prothrombin time, serum albumin to the list of blood tests to be conducted at screening	To determine Child-Pugh score
	Added serum magnesium and thyroid stimulating hormone (TSH) to the list of blood tests to be conducted at screening	To screen for increased risk of arrhythmia
5.3.1. Meals and Dietary Restriction	Participants will be provided a standard snack Changed to Participants will abstain from eating from the beginning of each visit until the final PK blood sample collection is completed. Consumption of water is permitted.	To minimize the potential variable of the presence or absence of a snack between subjects
8. Study Assessments and Procedures; Period 1 and Period 2 Evaluation Day	Deleted Offer a standard snack (Ensure or equivalent...)	To minimize the potential variable of the presence or absence of a snack between subjects

Section # and Name	Description of Change	Brief Rationale
1.3. Schedule of Activities (SoA) – Footnote 6.5 Concomitant Therapy 8. Study Assessments and Procedures	Added Lifetime history of medication taken for DM1 or sleep [will be recorded]	To reflect the intended collection of the medication history information
8. Study Assessments and Procedures	Increased blood volume collection values	To account for the lab tests added in this amendment
8. Study Assessments and Procedures; End of Study or Early Termination	Deleted The end of study or early termination evaluations may be conducted through a home health service and phone call with site staff	Removed due to lack of operational feasibility
1.2 Schema	Added to the procedures and assessments listed in the schema	Clarification
1.3. Schedule of Activities (SoA)	Added check mark for Urinalysis to End of Study	Correct inconsistency versus Section 8
	Added Spirometry to obtain FVC value to pulmonary function test	Clarification of the test to be administered
1.3. Schedule of Activities (SoA) - Footnote	Added Fasting is not required	Clarification
8. Study Assessments and Procedures	Added text throughout to specify order of outcomes measure tests	Clarification
8. Study Assessments and Procedures; Screening Visit 1	Added Spirometry to obtain FVC value to pulmonary function test	Clarification of the test to be administered
8.2.4 Clinical Safety Laboratory Assessments	Added Fasting is not required for the clinical laboratory tests	Clarification
10.2 Appendix 2: Clinical Laboratory Tests	Added Fasting is not required for the clinical laboratory tests	Clarification
10.3.3. Assessment of Causality - First Bullet	Added (Related or Unrelated)	Clarification
Throughout Protocol	Minor editorial and document formatting revisions	Minor, therefore have not been summarized

**SUMMARY OF CHANGES FOR VERSION 1.1, ORIGINAL**

Section	Revisions
Title page	Revised Study Phase from “2” to “1b”.
Summary of Changes for Version 1.1	Added.
1.1 Synopsis, Overall Design	Revised “1 week washout” to “4 to 8 days washout”.
1.1 Synopsis, Number of Participants	Revised number of participants from “a total of up to 12” to “a total of up to 14”.
1.1 Synopsis, Intervention Groups and Duration	Revised text as follows: - “1 week washout” to “4 to 8 days washout”. - “The follow up period is 7 days” to “The follow up period is approximately 4 to 8 days”.
1.2 Schema, Column Titles	Changed “Day” to “Period” and added “Washout 4-8 days”.
1.3 Schedule of Activities (SoA), Table Column Titles	Changed “Day” to “Period” and revised Washout Period from “Days 2-7” to “4-8 days”.
4.1 Overall Design	Revised “1 week washout” to “4 to 8 days washout”.
4.2 Scientific Rationale for Study Design, Last Paragraph	- Revised from “one week” to “approximately 4 to 8 days”. - Revised Study Phase from “2” to “1b”.
5.3.1 Meals and Dietary Restrictions	Revised “provided” to “offered”.
6. Study Intervention	Revised “a one-week” to “approximately 4 to 8 days”.
8. Study Assessments and Procedures, Period 1 and Period 2 Evaluation Day	- Deleted “(Day 1 and 8)”. - Revised “Allot randomization number (Day 1 only)” to “Allot randomization number (Period 1 only)”. - Revised “Subjects will be ... (approximately 7 [±1] days after Period 1), and for End-of-Study visit (after approximately 7 [±1] days after Period 2).” to “Subjects will ... (approximately 4 to 8 days after Period 1), and for End-of-Study visit (after approximately 4 to 8 days after Period 2).”
8. Study Assessments and Procedures, End of Study or Early Termination	- Revised “which will be conducted on Day 7 (+1 day) after Period 2” to “which will be conducted approximately 4 to 8 days after Period 2”. - Added “The end of study or early termination evaluations may be conducted through a home health service and phone call with site staff.”

**SUMMARY OF CHANGES FOR VERSION 1.1, ORIGINAL**

Section	Revisions
8.2 Safety Assessments, second paragraph	Revised from “End-of-Study evaluation (Day 7±1 day after Period 2)” to “End-of-Study evaluation (approximately 4 to 8 days after Period 2)”.
8.3.1 Time Period and Frequency for Collecting AE and SAE Information	Deleted “Medical occurrences that...not the AE section.”
10. Supporting Documentation and Operational	Revised section title from “10. SUPPORTING DOCUMENTATION AND OPERATIONAL” to “10. APPENDICES”.
10.3.1 Definition of AE, Events Meeting the AE Definition	Deleted “‘Lack of efficacy’...definition of an AE or SAE.’ and “The signs, symptoms,...constitutes an AE or SAE.”.

To: [REDACTED]

From: [REDACTED]  
[REDACTED]

Date: February 14, 2020

Subject: Study ERX-963-001 Tables, Listings, and Figures Delivery

This memo is to confirm that the tables, listings, and figures (TLFs) described in the text of the Statistical Analysis Plan (SAP) for Study ERX-963-001 will be produced and delivered as two separate deliveries.

The first delivery will include all TLFs, except for the ones specified below as belonging to the second delivery. Formats and additional specifications for the TLFs in the first delivery will be appended to the text of the SAP prior to study treatment unblinding. The TLFs in the first delivery will be produced and provided to Expansion Therapeutics after study treatment unblinding, according to a time schedule to be agreed between Innovative Analytics and Expansion Therapeutics. These TLFs will form the basis for the study clinical study report. Second delivery TLFs will be included in an addendum to the study clinical study report.

The second delivery includes TLFs that are not directly related to the primary or secondary study objectives. Formats and additional specifications for these TLFs will be created after study treatment unblinding. The schedule for the production of these formats and specifications, along with the schedule for the production of these TLFs shall be established by Innovative Analytics and Expansion Therapeutics after study treatment unblinding. Any additions or subtractions from the second delivery will also be determined at that time.

The TLFs to be included in the second delivery will be:

1. Summaries and listings of baseline Myotonic Dystrophy Health Index
2. TLFs related to electroencephalogram measurements
3. TLFs related to correlation of [REDACTED] concentrations with efficacy measurements
4. Listings of compartmental plasma pharmacokinetic parameters

To: [REDACTED]

Date: April 2, 2020

Subject: Study ERX-963-001 Tables, Listings, and Figures Delivery

This memo is to confirm the analyses and final tables, listings, and figures (TLFs) to be delivered for the Study ERX-963-001. This memo supersedes the memo issued on February 14, 2020 and will be attached to the Statistical Analysis Plan (SAP) Text, Version 1.0, December 6, 2019.

The Primary objective of the study is an assessment of the safety and tolerability of ERX-963 compared to placebo; accordingly, the TLFs of safety and tolerability will be produced and delivered. A subset of TLFs for the Secondary objective endpoints of the effect of ERX-963 compared to placebo will be produced and delivered. These TLFs will be the basis of the final Clinical Study Report (CSR). The pharmacokinetic analysis of Cohort 1 will be provided as separate report to be included as an appendix to the CSR.

The specific TLFs that are removed from the SAP Mockups, Version 1.0, February 7, 2020, are highlighted in yellow in Attachment A. The tables without highlighting will be included in the clinical study report.

In the memo issued on February 14, 2020, the following TLFs were specified to be delayed until a later analysis delivery or clinical study report addendum. These TLFs will no longer be created nor contained in any part of the Clinical Study Report:

1. Summaries and listings of baseline Myotonic Dystrophy Health Index
2. TLFs related to electroencephalogram measurements
3. TLFs related to correlation of [REDACTED] concentrations with efficacy measurements
4. Listings of compartmental plasma pharmacokinetic parameters

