#### 9.4.1. Efficacy Analyses

Endpoint	Statistical Analysis Methods
Primary	N/A
Secondary	PVT, SSS, One-back test, CGI-I, PGI-I
Exploratory	Will be described in the statistical analysis plan finalized before database lock.

Descriptive statistics will be computed for PVT, SSS, One-back test, EEG, CGI-I and PGI-I parameters.

For PVT, three variables will be analyzed: the number of attentional lapses, the reciprocal of the longest 10% response time (1/RT) of each trial, and the median reaction time.

For SSS, the analysis variable will be the numerical rating of sleepiness.

For the One-back test, the analysis variable will be the proportion of correct responses (the arcsine transformation of the square root will be used for analysis).

For each PVT, SSS, and One-back test efficacy variable, data will be reported for the pre-dose baseline and each time point of the study period. Differences from pre-dose baseline will be calculated for each time point as well as the median change over the two-hour study period for each participant. Changes from baseline for each patient on [REDACTED] will be compared to their placebo experience.

Cohort 1 and Cohort 2 data will be combined to assess the secondary efficacy parameters.

- A mixed effect model will be used to compare efficacy effects (PVT, SSS, and One-back test) following ERX-963 (IV [REDACTED] vs placebo. The model will include cohort, sequence, cohort-by-sequence interaction, treatment, treatment period, pre-dose baseline, measurement time point, measurement time-by-baseline interaction, and measurement time-by-treatment interaction as fixed effects, with subject (within cohort and sequence) as a random effect. The test statistic will be based on the treatment effects (experimental vs. placebo, averaged across the post-dose measurements), using the equally weighted mean of the Cohort 1 and Cohort 2 treatment effects.
- For CGI-I and PGI-I, the difference between the experimental and placebo responses will be estimated using a model with terms for cohort, sequence, cohort-by-sequence interaction, treatment, and treatment period as fixed effects, and with subject within cohort and sequence as a random effect. The test statistic will be based on the average of the treatment effects in Cohort 1 and Cohort 2.

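### The April 2020 memo replaces delivery of all secondary-endpoint outputs described in the SAP with a subset; the summary and model analyses of all five secondary instruments should stay committed.

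*SAP*

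**What the plan says.** **February 14, 2020 memo (front of the SAP).** It covers the tables, listings and figures (TLFs) described in the SAP text and splits them into two deliveries: "The first delivery will include all TLFs, except for the ones specified below as belonging to the second delivery". The first delivery is the basis of the CSR. Four groups go to the second: baseline MDHI, EEG, concentration-efficacy correlation, and compartmental PK listings. The memo says of them: "The second delivery includes TLFs that are not directly related to the primary or secondary study objectives". Formats for the first delivery "will be appended to the text of the SAP prior to study treatment unblinding". Later change is foreseen for the second delivery only: "Any additions or subtractions from the second delivery will also be determined at that time".

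**April 2, 2020 memo.** It supersedes the February memo and is to be attached to SAP Text Version 1.0. Safety and tolerability TLFs are kept. For efficacy it says: "A subset of TLFs for the Secondary objective endpoints of the effect of ERX-963 compared to placebo will be produced and delivered". It identifies what goes: "The specific TLFs that are removed from the SAP Mockups, Version 1.0, February 7, 2020, are highlighted in yellow in Attachment A". Of the four deferred groups it says: "These TLFs will no longer be created nor contained in any part of the Clinical Study Report".

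**Protocol 9.4.1 and SAP 14.** The Protocol plans descriptive statistics for all five secondary instruments and states: "A mixed effect model will be used to compare efficacy effects (PVT, SSS, and One-back test) following ERX-963". It plans a parallel model for CGI-I and PGI-I. SAP 14.2-14.5 gives SAS code for each instrument, and SAP 14 names PGI-I and SSS in advance as the variables most likely to respond.

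**Protocol 9.5 and SAP 17.** An efficacy analysis unblinded to the sponsor is planned once Cohort 1 has completed, and a further one is allowed. Both are described as administrative.

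**The concern.** The February memo, read with SAP 14, committed the sponsor to a full set of secondary efficacy outputs. The April memo shrinks that set. February gave no room for this, because its allowance for later subtractions covers only the second delivery, which holds nothing tied to the secondary objectives.

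Sample size is not the issue; completeness is. The trial has about six participants per cohort and is not powered for efficacy, so a partial display of efficacy results is easily misread. The sponsor may have seen unblinded efficacy data before the end of the study. If an analysis named in Protocol 9.4.1 is then missing from the CSR, a reader cannot tell whether it was dropped for scope or for its result.

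**Working it through.** The plan gives no figure to reproduce. The check sets the two memos side by side and counts outputs by hand from the mock-up contents.

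**Step 1. What changed.**

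| | February 14 memo | April 2 memo |
|---|---|---|
| Safety outputs | all in the CSR | all in the CSR |
| Secondary outputs described in the SAP text | all in the CSR | a subset, itemised in Attachment A |
| Four deferred groups | later addendum, open to change | cancelled |

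The second row is the point. The third row is a lesser matter: none of those groups serves a primary or secondary objective, and February foresaw changes to them.

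**Step 2. Secondary-endpoint outputs in the mock-up contents.**

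- Tables 14.2.2.1 to 14.2.2.13: 13
- Figures 14.2.2.2 to 14.2.2.7: 6
- Listings 16.2.6.3 to 16.2.6.7: 5
- Individual plots, Figures 16.2.6.2 and 16.2.6.3: 2

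Total: 13 + 6 + 5 + 2 = 26.

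**Step 3. Which of the 26 are written in SAP 14.1-14.5.**

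| Instrument | Summary table | Model table | Figures | Total |
|---|---|---|---|---|
| PVT | 14.2.2.1 | 14.2.2.2 | 14.2.2.2, 14.2.2.3, 14.2.2.4, 16.2.6.2 | 6 |
| SSS | 14.2.2.4 | 14.2.2.5 | 14.2.2.5, 16.2.6.3 | 4 |
| One-back | 14.2.2.7 | 14.2.2.8 | none | 2 |
| CGI-I | 14.2.2.10 | 14.2.2.11 | 14.2.2.6 | 3 |
| PGI-I | 14.2.2.12 | 14.2.2.13 | 14.2.2.7 | 3 |
| Sum | 5 | 5 | 8 | 18 |

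The other 26 - 18 = 8 are three Best Response tables (14.2.2.3, 14.2.2.6, 14.2.2.9) and five listings.

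**Step 4. How many could go.** A subset means at least 1 of the 26 is removed. If the removals all lie among the 8 outputs outside SAP 14.1-14.5, none of the 18 is lost. At the other extreme all 18 are. The range is 0 to 18, and the readable text does not narrow it.

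**Step 5. What the Protocol itself needs.** The core is the 5 + 5 = 10 summary and model tables. Protocol 9.4.1 bases its test on the treatment effect averaged over the two cohorts. Counting one such test per variable gives PVT 3 + SSS 1 + One-back 1 + CGI-I 1 + PGI-I 1 = 7, assuming the single PVT model table holds all three PVT variables. For One-back, SAP 14.4 had already replaced the pooled model with Cohort 2 alone, so that departure from the Protocol predates the memo.

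**The case against.** **The memo does itemise the removals.** This stands. Attachment A marks each one, so the subset is not unspecified. The highlighting is simply not visible here, and anyone with the coloured attachment can settle the count.

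**The missing reason and blinding status cannot be held against the plan.** This largely stands. The readable April text gives neither, but the memo headings are redacted and some SAP pages are not available. The point therefore rests on the narrowed commitment, not on that silence.

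**Not every secondary output was committed.** This also stands. February covers what the SAP text describes, and the Best Response tables appear only in the mock-ups. If only these were dropped, nothing in SAP 14 is lost.

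**A reader might infer that results drove the cut.** The documents do not support this. They do not say whether or when the interim look took place, or when treatment was unblinded. The same memo cancels baseline MDHI outputs, which are not a treatment outcome, and mentions a PK report for Cohort 1 only. That pattern also fits a general reduction in scope.

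**A reader might also infer that the CGI-I and PGI-I model tables were removed,** because they are among the entries that appear in bold in the mock-up contents. Bold may be a trace of the highlighting, but section headings are bold too, so it proves nothing.

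**The stakes are low.** This stands in part. Efficacy is secondary and unpowered, which limits the weight of the point. It does not make a partial efficacy display easier to read correctly.

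**Conclusion.** The concern holds in a limited form. The April memo withdraws February's commitment to deliver all secondary-endpoint outputs described in the SAP text and puts a subset in its place. Between 0 and 18 of the 18 outputs written in SAP 14.1-14.5 could be lost. Only if one of the 10 summary or model tables is removed does the CSR depart from both Protocol 9.4.1 and SAP 14. In that case the planned sponsor-unblinded efficacy looks mean that selective reporting could not be ruled out.

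The counts assume that the mock-up titles match the analyses described in the SAP text. They measure exposure, not bias: counting tables or contrasts says nothing about the direction or size of any distortion. The documents do not show selection by result. The safety outputs, which serve the primary objective, are unaffected. This is a cheap improvement.

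**What to change.** In the April 2, 2020 memo, replace the sentence on the subset with:

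> The summary and model analyses in SAP 14.1-14.5 for all five secondary instruments (PVT, SSS, One-back, CGI-I, PGI-I) will be produced and included in the CSR. For One-back this means the Cohort 2 model, and summary statistics only for Cohort 1.

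Restore any of these that Attachment A removes. Figures, Best Response tables and exploratory outputs may stay out, provided the CSR lists them as planned but not produced, with the reason and the blinding status at the time of the decision. The same declaration would serve for any removed listing.

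The cost is modest programming and review time and a somewhat longer CSR. The model code and mock-ups already exist, and no new data are needed. If Attachment A removes none of the 10 tables, only the wording changes.
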